---

**CONFIDENTIAL**

This document is confidential and the property of The Cleveland Clinic Foundation. No part of it may be transmitted, reproduced, published, or used by other persons without prior written authorization from the study sponsor.

V6.0\_22May2017

Abbreviation of Term	Definition
AAD	Anti-Arrhythmic Drug
ACC	America College of Cardiology
ACE	Angiotensin Converting Enzyme
AE	Adverse Event
AF	Atrial Fibrillation
AFSS	Atrial Fibrillation Severity Scale
AHA	American Heart Association
ARB	Angiotensin Receptor Blocker
AVN ablation	Atrioventricular Node ablation
BP	Blood Pressure
CHF	Congested Heart Failure
CRF	Case Report Form
DC cardioversion	Direct Current cardioversion
ECG	Electrocardiogram
EF	Ejection Fraction
ESC	European Society of Cardiology
HF	Heart Failure
HR	Heart Rate
HRS	Heart Rhythm Society
ITT	Intent To Treat
LV	Left Ventricle
MRI	Magnetic Resonance Imaging
NYHA	New York Heart Association
PVI	Pulmonary Vein Isolation
RVR	Rapid Ventricular Response
SAE	Serious Adverse Event
SOC	Standard of Care

## Study Synopsis

Title	Catheter Ablation vs. Medical Therapy in Congested Hearts with AF (CATCH-AF in Patients with impaired LV function)
Protocol Number	6.0
Study Treatment	Strategy of Early Atrial Fibrillation Ablation compared to conventional Anti-Arrhythmic Drug management.
Indication	Chronically impaired LV function on optimal medical therapy with first encounter for new symptomatic AF diagnosis within 12 months.
Study Design	This study is a, multi-center, randomized, unblinded, clinical trial with the objective of enrolling 220 patients over approximately 18 months.
Study Objectives	
 
• To determine if catheter-based atrial fibrillation (AF) ablation is superior to medical treatment in patients with impaired left ventricular function who have been diagnosed with symptomatic AF within the past 12 months
 
• Hypothesis: AF ablation is better than medical therapy for patients with symptomatic AF and impaired LV function in terms of recurrent and total number of hospitalizations, recurrence of AF, EF, quality of life, and 6-minute walk distance.
 

Primary Endpoint	The primary endpoint is time to first hospitalization (>24hr) for heart failure, recurrence of AF or DC cardioversion after the treatment period
Secondary Endpoint	Secondary endpoints will include evaluation of the following: 
 
• Total number of cardiovascular hospitalizations during the trial period for each group
 
• Time to Recurrence of AF lasting longer than 30 seconds
 
• Change in distance walked in 6-minute walk test
 
• Change in Rand 36-Item Health Survey (SF-36) during trial period
 
• Change in EF during trial period
 

Duration of Treatment and Study Period	The time course for the trial is divided into a treatment period followed by the trial period. The treatment period will include the first 3 months post enrollment. The trial period will commence at end of treatment period and all outcome data will be collected over a 12 month period.

### CONFIDENTIAL

This document is confidential and the property of The Cleveland Clinic Foundation. No part of it may be transmitted, reproduced, published, or used by other persons without prior written authorization from the study sponsor.

V6.0\_22May2017

Inclusion Criteria	
Patients must meet all of the following criteria:
 
 
• Be <math>\geq 18</math> years of age
 
• Provide signed written Informed Consent
 
• Symptomatic AF documented by ECG or heart rhythm monitoring within 12 months.
 
• Patients should be on optimal medical therapy for HF (heart failure) for three months prior to randomization. Adjustments to medications within this 3 month period are permitted.
 
• Chronically impaired LV function defined as EF 20%-45% within the last 3 months by echocardiogram, nuclear imaging, MRI or cardiac catheterization
 
• All patients should be on an optimal therapy for impaired LV function. Optimal therapy includes at least one ACE inhibitor or angiotensin receptor blockers (ARB) in ACE-intolerant patients along with beta blockers for at least 3 months. For those patients intolerant to ACE/ARB's, a combination of hydralazine and isosorbide dinitrate is recommended. NYHA class III patients may be prescribed spironolactone
 
• Ability to complete 6 minute walk test
 
• Be eligible for catheter ablation and anti-arrhythmic drugs
 

--------------------	--

**CONFIDENTIAL**

This document is confidential and the property of The Cleveland Clinic Foundation. No part of it may be transmitted, reproduced, published, or used by other persons without prior written authorization from the study sponsor.

V6.0\_22May2017

Exclusion Criteria	
Patients must meet none of the criteria:
 
 
• Women of childbearing potential (women will not be permitted to participate unless post-menopausal or surgically sterile)
 
• Patients hospitalized for HF (heart failure) within the 3 months prior to randomization
 
• Reversible causes of AF such as pericarditis, thyroid disorders, acute alcohol intoxication, recent major surgical procedures, or trauma
 
• Recent Reversible LV impairment that may be attributed to AF with RVR and may improve with introduction of rate control.
 
• Presently with Valvular Heart disease requiring surgical intervention
 
• Presently with coronary artery disease requiring surgical or percutaneous intervention
 
• Early Post-operative AF (within three months of surgery)
 
• Previous MAZE or left atrial instrumentation (including ablation and Left Atrial Appendage exclusion)
 
• History of AVN ablation
 
• Hypertrophic Cardiomyopathy
 
• Prolonged QT interval
 
• Liver Failure
 
• Renal Failure requiring dialysis
 
• Social factors that would preclude follow up or make compliance difficult. History of drug, alcohol, or substance abuse as assessed by the investigator.
 
• Contraindication to the use of anti-arrhythmic medications and/or appropriate anticoagulation therapy
 
• Currently enrolled in, or discontinued within the last 30 days from, a clinical trial involving an investigational product or non-approved use of a drug or device or concurrently enrolled in any other type of medical research judged not to be scientifically or medically compatible with this study.
 
• Patients with severe pulmonary disease
 
• Documented intra-atrial thrombus, tumor, or another structural abnormality which precludes catheter introduction
 
• Unable or unwilling to comply with protocol requirements or deemed by the investigator to be unfit for the study.
 

Study Product, Dose, Route, Regimen	Patients will be randomized in a 1:1 fashion (based on EF stratification EF $\leq$ 35% and >35%) into treatment by AF ablation or AADs.
Statistical Methodology	Sample size is based on an expected 30-40% AF recurrence rate at 12 months in the ablation arm and a 60% AF recurrence rate at 12 months in the AADs. One hundred patients per treatment arm are needed to have 80% power at an alpha level of 0.05 to detect this difference. Assuming a 10% drop-out rate, a total of 220 patients will need to be enrolled. Randomization will be 1:1 based on EF stratification EF $\leq$ 35% and >35%. A Cox proportional hazards regression model adjusting for site and EF strata will be used to test for treatment group differences in the primary endpoint.

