## Study Assessments:

Procedure	Screening/ Baseline/ Randomization Visit	3-6 month Follow-up Visit (+/- 3 weeks)	12-15 month Follow-up Visit (+/- 3 weeks)
Confirm Inclusion/Exclusion Criteria	X		
Obtain Informed Consent	X		
Verify that females are not of childbearing potential 	X		
Randomization	X		
Record Medical History and Physical	X		
Record Vital Signs HR/BP	X	X	X
Record Medications	X	X	X
Record ECG	X	X	X
Record Echocardiogram	X		X
6 minute walk test	X	X	X
Record Routine Lab Assessments	X	X	X
Record Clinically Indicated Tests	X	X	X
Rand 36-Item Health Survey (SF-36)	X	X	X
AFSS QOL	X	X	X
Assessment NYHA	X	X	X
Arrhythmia Monitoring	X	X	X
Assessment of SAE/AE		X	X
Assessment of Hospitalization		X	X

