### 3.1 Primary Endpoint

Time to first hospitalization (> 24 hours) for Heart Failure, recurrence of AF or DC cardioversion after the treatment period

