### 6.3 Baseline Visit

Baseline visit assessments will be completed for both arms before initiation of treatment. These include:

1. Record vital signs (HR and BP)
2. Record demographic and medical history information
3. For female subjects: Verify that the subject is post-menopausal /surgically sterile following individual site standard of care process
4. Record use of select medications
5. Record 12 lead ECG results
6. Record Echocardiogram results
7. Perform 6 minute walk test
8. Collect Rand 36-Item Health Survey (SF-36)
9. Collect Atrial Fibrillation Severity Scale (AFSS)
10. Assessment of NYHA class
11. Record the data from remote arrhythmia monitoring and /or ECGs completed as a part of standard of care
12. Record results from routine lab assessment and clinically indicated tests completed as a part of standard of care; these may include but not limited to:
  - Laboratory assessments may include CBC, PT, PTT, INR if applicable, chest x-rays, pulmonary function test, spiral CT to assess pulmonary vein stenosis (only if in the ablation arm)

CONFIDENTIAL

This document is confidential and the property of The Cleveland Clinic Foundation. No part of it may be transmitted, reproduced, published, or used by other persons without prior written authorization from the study sponsor.

V6.0\_22May2017

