## 7 Statistical Analysis

A Cox proportional hazards regression model adjusting for site and randomization strata will be used to test for treatment group differences in the primary endpoint. Kaplan-Meier estimates and curves will also be created. Secondary endpoints will be analyzed using a two-sample t-test or Wilcoxon signed rank as appropriate. Depending on the distribution for the total number of hospitalizations it will be treated as a continuous variable or collapsed into categories (0-2, 3-5, 5-7, >7). The intent-to-treat population will be used for all analysis. Patients who drop-out before study completion due to cardiac causes will be considered as having an event at the time drop-out for the primary analysis. Patients who drop-out for other reasons will be treated as censored observations at the time of drop-out in the primary analysis. Analysis based on the protocol and safety populations will also be done. All statistical tests will be two-sided and an alpha of 0.05 or less will be considered statistically significant. Mean and

CONFIDENTIAL

This document is confidential and the property of The Cleveland Clinic Foundation. No part of it may be transmitted, reproduced, published, or used by other persons without prior written authorization from the study sponsor.

V6.0\_22May2017

standard deviation or frequency and percent will be used to describe demographics, medical history and other baseline variables by treatment group. T-tests or chi-square tests as appropriate will be used to compare the baseline factors by treatment group.

Sample size is based on an expected 30-40% rate of hospitalization for recurrence of AF, heart failure or DC conversion at 12 months in the ablation arm and a 60% rate at 12 months in the AAD arm. One hundred patients per treatment arm are needed to have 80% power at an alpha level of 0.05 to detect this difference. Assuming a 10% drop-out rate, a total of 220 patients will need to be enrolled. Randomization will be 1:1 based on EF stratification EF  $\leq$ 35% and >35%.

**Safety population:** All patients that received any ablation treatment **or at least 1 dose of AAD** will be included in the safety population.

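### Baseline NYHA class is scheduled in both arms but unused in the primary Cox model; prespecifying it as a covariate would be a cheap improvement to a valid analysis

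*Combined protocol and SAP*

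**What the plan says.** Both descriptions of the primary analysis name the same covariates. The synopsis (Statistical Methodology) has "A Cox proportional hazards regression model adjusting for site and EF strata will be used to test for treatment group differences". Section 7 has "A Cox proportional hazards regression model adjusting for site and randomization strata will be used", where the only stratification factor is EF at or below 35% v above 35% (Section 5.4).

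The endpoint in Section 3.1 is "Time to first hospitalization (> 24 hours) for Heart Failure, recurrence of AF or DC cardioversion after the treatment period", so heart-failure hospitalization is one of three components. Section 7 also counts drop-out for cardiac causes as an event.

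NYHA class appears in the Study Assessments table ("Assessment NYHA") and in Section 6.3 ("Assessment of NYHA class"). On timing, Section 6.3 says "Baseline visit assessments will be completed for both arms before initiation of treatment". NYHA is not a stratification factor, a model term or an endpoint. Eligibility sets no NYHA limit, and inclusion criterion 6 mentions class III patients, so a mix of classes can be expected. Section 7 compares baseline factors between arms but does not say what follows if they differ. It describes no sensitivity analysis with further covariates.

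**The concern.** NYHA class grades functional limitation. EF measures pump function and enters the model only as a single cut at 35% within an eligible range of 20-45%. Two patients in the same EF stratum can therefore differ in NYHA class and, plausibly, in their risk of a heart-failure admission.

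If NYHA is prognostic for the composite, leaving it out of a Cox model has two consequences. The treatment hazard ratio is averaged over NYHA classes, which puts it somewhat nearer 1 and costs some power. In addition, if the arms differ by chance in NYHA mix, the model can correct only the part that EF stratum and site explain.

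There is also a question of process. The trial is unblinded and Section 7 tests baseline differences. Adding NYHA after seeing that table would be a post hoc choice, open to challenge in either direction.

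**Working it through.** **Inputs from the documents.** Two-sided alpha 0.05; 100 per arm for 80% power; 12-month event rates of 60% (drug arm) and 30-40% (ablation arm); 12 months of endpoint follow-up. The 40% end drives the sample size, since 30% v 60% would need only 42 per arm.

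**Inputs assumed.** Share of patients in the higher NYHA class, 30-50%; NYHA hazard ratio on the composite, 1.0 to 3.0. The documents give neither.

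**1. The plan's own figure.** For two proportions, n per arm = [1.96 x sqrt(2 x 0.5 x 0.5) + 0.8416 x sqrt(0.4 x 0.6 + 0.6 x 0.4)]^2 / 0.2^2 = (1.386 + 0.583)^2 / 0.04 = 97, against 100 stated. Power at 100 per arm is 81.2%. On the survival scale, HR = ln(0.6)/ln(0.4) = 0.557. Expected events = 100 x 0.4 + 100 x 0.6 = 100, and Schoenfeld's formula gives 83.2% power. The stated power is met with no covariate.

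**2. Power without and with NYHA.** Simulated exponential event times, overall rates held at 40% and 60%, 100 per arm, binary NYHA, Cox Wald test, 6000 runs per scenario:

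| NYHA HR | Share 30% | Share 40% | Share 50% |
|---|---|---|---|
| 1.0 | 82.8 to 82.7% | not run | 81.5 to 81.4% |
| 1.25 | 83.0 to 83.1% | not run | 82.2 to 82.7% |
| 1.5 | 82.9 to 83.7% | 81.8 to 82.6% | 82.5 to 83.7% |
| 2.0 | 83.1 to 85.6% | 83.4 to 86.0% | 82.7 to 85.4% |
| 2.5 | not run | 82.8 to 87.9% | not run |
| 3.0 | 83.4 to 88.5% | not run | 83.3 to 89.2% |

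The Monte Carlo standard error is about 0.5 point per figure, and smaller for the paired difference. Under the null (share 40%, NYHA HR 2), type I error is 5.1% without NYHA and 5.2% with it.

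**3. How often the arms differ.** The SD of the between-arm difference in the higher-class share q is sqrt(2q(1-q)/100), which is 0.065, 0.069 and 0.071 at q = 30%, 40% and 50%. The chance of a difference of 10 points or more, in either direction, is 12.3%, 14.9% and 15.7%. EF stratification lowers these figures if NYHA and EF are correlated.

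**4. What a 10-point difference does.** The approximate multiplier on the unadjusted treatment HR is [1 + (q + 0.05)(h - 1)] / [1 + (q - 0.05)(h - 1)], where h is the NYHA hazard ratio. At q = 40%:
- h = 1.25: 1.1125/1.0875 = 1.02
- h = 1.5: 1.225/1.175 = 1.04
- h = 2.0: 1.45/1.35 = 1.07
- h = 2.5: 1.675/1.525 = 1.10

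**5. Power when the difference runs against ablation.** With 45% higher class in the ablation arm, 35% in the drug arm and h = 2, simulated power is about 72-73% without NYHA and about 85-86% with it. The unadjusted treatment HR moves from about 0.55 to about 0.60. Half of the 12-16% in step 3, about 6-8% of randomizations, reach at least this size against ablation; a similar share flatters it.

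**Limits.** The simulations use a binary NYHA, proportional hazards, and no site or EF terms, so they approximate the comparison between the planned and the extended model. Correlation between NYHA and EF would shrink every gain.

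**The case against.** The strongest reply is that nothing is wrong. Adjusting for site and the randomization stratum is a sound primary analysis, randomization protects type I error, and the trial reaches its stated power without NYHA. This stands. A reader might infer that the omission leaves the trial underpowered; step 1 shows that it does not.

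A reader might also infer that imbalance in heart-failure severity goes uncorrected. The documents do not support that. EF is both a stratification factor and a model term. Eligibility limits EF to 20-45%, requires three months of heart-failure therapy and excludes recent heart-failure admission. Only the part of NYHA that EF and site do not explain is unadjusted.

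The prognostic strength of NYHA for this composite is unknown. Two of the three components concern AF recurrence and cardioversion, and the synopsis bases its rates on AF recurrence alone. If the NYHA hazard ratio is 1.25 or less, the average gain is close to nil. This stands too, and it is why the result is given as a range.

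The shift also needs scale. With 100 events the standard error of the log HR is about 2/sqrt(100) = 0.20, so a 7% shift (ln 1.07 = 0.068) is about one third of a standard error, and the confidence interval already allows for it on average. That is correct across repeated randomizations, but adjustment improves precision in the one that is carried out.

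Finally, Section 1.1 names AF type and AF duration, not NYHA, as related to outcome. That is a reason to consider those variables as well; it does not count against NYHA.

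**Conclusion.** The primary model is valid and adequately powered on the plan's own assumptions. Its one missed opportunity here is a scheduled baseline measure that may carry information about heart-failure admissions beyond the EF stratum.

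The average benefit is small: about 0-1 point of power for an NYHA hazard ratio up to 1.5, 2-3 points at 2 and about 5 at 2.5. The clearer benefit is protection in the minority of randomizations where NYHA mix differs by 10 points or more, together with settling the choice before the baseline table is seen. All sizes depend on an assumed NYHA share of 30-50% and an assumed effect on the composite, and they are upper figures if NYHA and EF are correlated. This is an optional refinement, not a defect, and the required sample size does not change.

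**What to change.** In Section 7 and in the synopsis, specify the primary Cox model as *adjusting for site, EF stratum and baseline NYHA class (I-II v III-IV)*. Keep the present site and EF model as a sensitivity analysis.

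Add to Section 6.3 that NYHA class is recorded before randomization. At present the Study Assessments table puts screening, baseline and randomization in one visit, and baseline assessments need only precede treatment. In an unblinded trial, a clinician-judged class could therefore be graded after the arm is known.

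The cost is a short text change made before unblinded data are analysed. No new assessment is needed, but sites must respect the order of recording. One more parameter is estimated from about 100 expected events. The treatment HR also becomes conditional on NYHA: in the simulations with an NYHA HR of 2, the conditional HR is 0.544, against 0.557 from the overall rates. The report should say which of the two it presents.

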## Study Assessments:

Procedure	Screening/ Baseline/ Randomization Visit	3-6 month Follow-up Visit (+/- 3 weeks)	12-15 month Follow-up Visit (+/- 3 weeks)
Confirm Inclusion/Exclusion Criteria	X		
Obtain Informed Consent	X		
Verify that females are not of childbearing potential 	X		
Randomization	X		
Record Medical History and Physical	X		
Record Vital Signs HR/BP	X	X	X
Record Medications	X	X	X
Record ECG	X	X	X
Record Echocardiogram	X		X
6 minute walk test	X	X	X
Record Routine Lab Assessments	X	X	X
Record Clinically Indicated Tests	X	X	X
Rand 36-Item Health Survey (SF-36)	X	X	X
AFSS QOL	X	X	X
Assessment NYHA	X	X	X
Arrhythmia Monitoring	X	X	X
Assessment of SAE/AE		X	X
Assessment of Hospitalization		X	X

**1. Verify that female subject is post-menopausal /surgically sterile following individual site standard of care process**

Note: Baseline assessments to be completed before assigned treatment initiated.

**If the above assessments are collected as part of routine care, please record the information on the Case Report Form (CRF) at the study visit time points. For the ablation arm, record date of ablation and target areas on the CRF.**

# 1 Introduction

## 1.1 Background

AF is the most prevalent arrhythmiai (Kannel, 1982) and its optimal management remains unclear. AF frequently complicates the management of patients with heart failure (HF) and rate control only strategy is not always possible or practical in this population. Furthermore, it is well recognized that HF begets AF, vice versa and in this particular population AF begets more AF, leading to AF prevalence rates as high as 50% in an elderly population with CHFii. The optimal treatment strategy for AF in this population, and clinical outcomes of these strategies, has not been well studied.

AF ablation has emerged as a highly effective way to abolish the triggers that initiate AF and thus provides an important treatment option for patients intolerant of AF, or those whose AF is refractory to standard therapies. We and others have published analyses of patients with impaired LV function treated with ablation and found ablation to be an effective and safe therapeutic option for this patient population as welliii. However this strategy is not widely adopted. Studies have shown that rate control remains a safe and effective means of managing AF. The results of the rate-control vs. rhythm-control trials might lead to the conclusion that sinus-rhythm restoration is of comparable efficacy while allowing patients to remain in AF with a controlled ventricular rateiv. A limitation of all these trials is that the rhythm-control strategy was not efficacious. Furthermore, in an analysis of a study that evaluated predictors of mortality, sinus rhythm was associated with a 47% reduction in the risk of death, whereas use of antiarrhythmic drug therapy was associated with a 49% increase in mortalityv. This suggests that the neutral results in the rate-control vs. rhythm-control trials might be explained by the fact that the benefits of antiarrhythmic drugs in restoring sinus rhythm were negated by offsetting detrimental effects of antiarrhythmic drug therapy. In theory, a therapy that restores and maintains sinus rhythm while avoiding the deleterious effects of antiarrhythmic drugs would improve survival. It is known that ablation and management of paroxysmal AF is much more successful than persistent AF. Also a longer history of AF and longer duration of AF episodes are associated with worse outcomes. In our practice it has also become more evident that early intervention with ablation may decrease the AF burden so that if ablation is performed early in the disease there is less opportunity for developing permanent AF with all its deleterious effects.

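### AF type (paroxysmal or persistent) is called a major determinant of treatment success, but it is not a named baseline item, a stratification factor or a term in the primary Cox model

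*Combined protocol and SAP*

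**What the plan says.** The rationale in section 1.1 treats AF type as a known determinant of success: "It is known that ablation and management of paroxysmal AF is much more successful than persistent AF". Inclusion criterion 3 in section 5.2 asks for symptomatic AF documented within 12 months. Neither it nor the exclusion list in section 5.3 limits the type of AF.

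The design and analysis sections do not return to AF type:

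- **Allocation.** Section 7: "Randomization will be 1:1 based on EF stratification", with two EF strata. The Study Synopsis and section 5.4 agree.
- **Baseline data.** Section 6.3 has "Record demographic and medical history information", and the Study Assessments table has "Record Medical History and Physical". Both also list ECG, arrhythmia monitoring and the AF severity scale. AF type is not named in either.
- **Primary model.** Section 7: "A Cox proportional hazards regression model adjusting for site and randomization strata will be used". The Synopsis describes the same model.
- **Imbalance.** T-tests or chi-square tests "will be used to compare the baseline factors by treatment group". No adjustment follows from them, and no subgroup or sensitivity analysis uses AF type.

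**The concern.** AF recurrence is part of the primary endpoint (section 3.1). A factor that the protocol ties strongly to treatment success therefore plausibly predicts that endpoint. Omitting a prognostic factor from a Cox model costs power. It also makes one particular result harder to read: if one arm has clearly more persistent AF, the unadjusted hazard ratio reflects both treatment and case mix.

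The baseline tests in section 7 might reveal such a difference, but the plan does not say what would then be done. In an unblinded trial, a covariate added after the data have been seen is open to challenge, whereas one named in advance is not.

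**Working it through.** **1. The plan's own figure.** Section 7 gives 60% events at 12 months on drugs, 30-40% on ablation, two-sided alpha 0.05, 80% power and 100 per arm. At 40% vs 60%, with mean 0.50:

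n = [1.960·√(2·0.50·0.50) + 0.842·√(0.40·0.60 + 0.60·0.40)]² / 0.20² = (1.386 + 0.583)² / 0.04 ≈ 97 per arm.

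Power at 100 per arm is Φ[(0.20·10 − 1.386)/0.693] = Φ(0.886) = 81%. The stated size is reproduced and rests on the 40% end of the range. The implied hazard ratio is ln(0.60)/ln(0.40) = 0.557. Expected events are 100·0.60 + 100·0.40 = 100.

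**2. Assumptions.** The documents give no share of persistent AF and no effect size. I took 30%, 50% and 70% for the share when looking at imbalance, 30% and 50% for power, and hazard ratios of 1.5, 2 and 3 for persistent vs paroxysmal AF.

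**3. Chance imbalance, 100 per arm.** The standard deviation of the between-arm difference is √(2q(1−q)/100): 0.071 at q = 0.5 and 0.065 at q = 0.3 or 0.7. The exact binomial probability of a difference of at least 10 points in either direction is 17.9% at q = 0.5 and 14.2% at q = 0.3 or 0.7. A normal approximation without continuity correction gives 15.7% and 12.3%. In the direction that disfavours ablation alone, the exact figures halve to 8.9% and 7.1%.

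**4. Power with and without AF type.** Simulated Cox models used 2,000 trials per setting, 100 per arm, exponential times, censoring at 12 months and marginal rates of 40% vs 60%. AF type acts on the hazard equally in both arms. Site, EF stratum and drop-out were left out.

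| Persistent-AF hazard ratio | Share persistent | Power without | Power with | Gain (points) | Unadjusted HR multiplied, per 10 points more persistent AF on ablation |
|---|---|---|---|---|---|
| 1.5 | 30% | 82.4% | 83.7% | 1.3 | 1.04 |
| 1.5 | 50% | 84.3% | 84.9% | 0.6 | 1.04 |
| 2 | 30% | 82.9% | 85.6% | 2.7 | 1.08 |
| 2 | 50% | 82.5% | 84.6% | 2.1 | 1.07 |
| 3 | 30% | 82.6% | 89.8% | 7.2 | 1.12 |
| 3 | 50% | 82.4% | 88.6% | 6.2 | 1.10 |

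The Monte Carlo standard error of each power is about √(0.83·0.17/2000) = 0.8 points.

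**5. Type I error.** With no treatment effect, rejection was 4.2% to 5.6% across all settings, with or without the term.

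**6. When the imbalance goes against ablation by 10 points or more.** Power without and with the term was 68-71% vs 83-85% at a hazard ratio of 2, and 56-65% vs 90-91% at 3. Each cell rests on 110 to 161 trials, so these figures are uncertain by about 4 points. Imbalances in ablation's favour offset them in the overall averages of step 4.

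**The case against.** The other side has a good deal on its side.

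- **The planned analysis is conventional and valid.** Adjusting for site and the stratification factor is a recognised choice, and EF is a defensible single stratifier in an impaired-LV trial. Randomization covers chance imbalance on average, as step 5 confirms. This stands. A reader might infer that the primary result would be biased or the test invalid; the documents do not support that.
- **The gain is modest.** Simulated power without the term never falls below the 80% target, and only an assumed hazard ratio of 3 gives a sizeable gain. At 35% or 30% events on ablation, two-proportion power at 100 per arm is already 95% or 99%. This stands, and it makes the point an inexpensive improvement rather than a repair.
- **The protocol does not rank predictors.** Section 1.1 gives no effect size and does not define success. A reader might take AF type to be the strongest predictor of the composite endpoint, but that goes beyond the text.
- **Not named is not the same as not collected.** The case report form is not among the documents, and the history item may already cover AF type. Pre-treatment ECG and monitoring records would also allow later classification. It would therefore be wrong to say that the data are missing or irrecoverable.
- **AF duration.** Section 1.1 also says: "Also a longer history of AF and longer duration of AF episodes are associated with worse outcomes". A reader might extend the point to time since diagnosis. Section 5.1 limits enrolment to a new diagnosis within 12 months, which already narrows that range, so the case for a second covariate is weak.
- **Hazard ratios with and without the term.** At a persistent-AF hazard ratio of 3, the treatment hazard ratio averages 0.55 without the term and 0.52 with it. That gap is largely the difference between a marginal and a conditional hazard ratio, not an error in the planned estimate.

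None of this supplies a pre-specified use of AF type, which is what remains.

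**Conclusion.** The point holds as a low-cost improvement in efficiency and pre-specification. The protocol attaches large importance to AF type and admits both types, but neither balances nor adjusts for it and does not name it as a baseline item.

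Under the stated assumptions the average cost is about 1 to 7 points of power. At the lower end (hazard ratio 1.5) it is close to negligible; at the upper end (hazard ratio 3) it is worth having. About one trial in six or seven would show an imbalance of 10 points or more. Each 10 points would move the unadjusted hazard ratio by about 4% to 12%, with no agreed way to handle it.

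These sizes depend on the assumed share and effect of persistent AF, on the 40% vs 60% scenario, and on an equal effect of AF type in both arms. If section 1.1 instead means that the benefit of ablation itself differs by AF type, a main-effect term would not capture that.

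**What to change.** 1. In the Study Assessments table and section 6.3, name AF type (paroxysmal or persistent) as a baseline field, recorded before randomization so that knowledge of the assigned arm cannot influence it. If the case report form already captures it, this step only documents existing practice.
2. In the Synopsis (Statistical Methodology) and section 7, describe the primary model as a Cox model *adjusting for site, EF stratum and baseline AF type*. Fix this before outcome data are examined, and do not make it depend on the baseline significance tests.

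The cost is at most one form field drawn from the history already taken, and one model degree of freedom against about 100 expected events. The treatment hazard ratio becomes conditional on AF type, and the report should say so. The planned Kaplan-Meier curves can stay as they are. Neither the sample size nor the randomization scheme needs to change.
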